5.3 Exclusion Criteria

Yes/No (Response of “yes” = patient ineligible)

5.3.1 Prior chemotherapy for metastatic urothelial carcinoma.

5.3.2 Prior chemotherapy for localized urothelial carcinoma that has been completed less than 6 months before registration.

5.3.3 Variant histologies other than urothelial carcinoma will not be allowed. Patients with a component of variant histologies will be allowed to enroll, if urothelial carcinoma is the predominant histology per investigator judgement. Patients with any component of small cell will be excluded.

5.3.4 Has received prior treatment with cabozantinib.

5.3.5 Receipt of any type of small molecule kinase inhibitor (including investigational kinase inhibitor) within 2 weeks before first dose of study treatment.

5.3.6 Receipt of any type of cytotoxic, biologic, or other systemic anticancer therapy (including investigational) within 4 weeks before first dose of study treatment.

5.3.7 Has received prior therapy with an anti-PD-1, anti-PD-L1, or anti-PD-L2 agent or other checkpoint inhibitors previously.

5.3.8 Radiation therapy for bone metastasis ≤ 2 weeks, any other radiation therapy within 4 weeks before first dose of study treatment. Systemic treatment with radionuclides within 6 weeks before the first dose of study treatment. Subjects with clinically relevant ongoing complications from prior radiation therapy are not eligible.

5.3.9 Has known active central nervous system (CNS) metastases and/or carcinomatous meningitis. Subjects with previously treated brain metastases may participate provided they are stable (without evidence of progression by imaging for at least 4 weeks prior to the first dose of trial treatment and any neurologic symptoms have returned to baseline), have no evidence of new or enlarging brain metastases, and are not using steroids for at least 7 days prior to trial treatment. This exception does not include carcinomatous meningitis which is excluded regardless of clinical stability.

5.3.10 Concomitant anticoagulation with oral coagulants except for those specified below.

Allowed anticoagulants are the following:

- Prophylactic use of low-dose aspirin for cardio protection (per local applicable guidelines)
- Low-dose low molecular weight heparins (LMWH)
- Therapeutic doses of LMWH or anticoagulation with direct factor Xa inhibitors rivaroxaban, edoxaban, or apixaban is allowed in subjects without known brain metastases who are on a stable dose of the anticoagulant for at least 1 week before the first dose of study treatment without clinically significant hemorrhagic complications from the anticoagulation regimen or the tumor.

5.3.11 _____ The subject has prothrombin time (PT)/INR or partial thromboplastin time (PTT) test $\geq 1.3 \times \text{ULN}$ within 14 days before the first dose of study treatment.

5.3.12 _____ The subject has uncontrolled, significant intercurrent or recent illness including, but not limited to, the following conditions:

- Cardiovascular disorders:
 - Ongoing congestive heart failure exacerbation or New York Heart Association Class 4, unstable angina pectoris, serious cardiac arrhythmias.
 - Uncontrolled hypertension defined as sustained blood pressure (BP) $> 150 \text{ mm Hg}$ systolic or $> 100 \text{ mm Hg}$ diastolic despite optimal antihypertensive treatment. Uncontrolled hypertension needs to be determined based on persistently high blood pressure readings over more than 24 hours and should NOT be based on the blood pressure readings from one clinic visit. Blood pressure readings done at home or by primary care providers are acceptable. If a blood pressure reading on the day of screening is high, but there are documented acceptable ($\leq 150 \text{ mm Hg}$ systolic and $\leq 100 \text{ mm Hg}$ diastolic) blood pressure readings prior to or after the screening visit (with or without the use of anti-hypertensive medications), patient will not be considered to have uncontrolled hypertension.
 - Stroke (including transient ischemic attack [TIA]), myocardial infarction (MI), or other ischemic event, or symptomatic thromboembolic event (e.g., deep venous thrombosis, pulmonary embolism) occurring less than or equal to 6 months before first dose of cabozantinib. [Note: Subjects with a diagnosis of deep vein thrombosis (DVT) or incidentally detected asymptomatic and sub-segmental pulmonary embolism (PE) on routine scans are allowed if on a stable dose of anti-coagulation for at least 1 week before first dose of study treatment]
 - Clinically significant hematuria, hematemesis, or hemoptysis of > 0.5 teaspoon (2.5 ml) of red blood, or other history of significant bleeding (e.g., pulmonary hemorrhage) within 12 weeks before first dose.

- Gastrointestinal (GI) disorders including those associated with a high risk of perforation or fistula formation:
 - The subject has evidence of tumor invading the GI tract, active peptic ulcer disease, inflammatory bowel disease (e.g., Crohn's disease), diverticulitis, cholecystitis, symptomatic cholangitis or appendicitis, acute pancreatitis, acute obstruction of the pancreatic duct or common bile duct, or gastric outlet obstruction.
 - Abdominal fistula, GI perforation, bowel obstruction, or intra-abdominal abscess within 6 months before first dose.

Note: Complete healing of an intra-abdominal abscess must be confirmed before first dose.

- Cavitating pulmonary lesion(s) or known endotracheal or endobronchial disease manifestation.
- Lesions invading or encasing any major blood vessels.
- Other clinically significant disorders that would preclude safe study participation per investigator clinical judgement.
 - Serious non-healing wound/ulcer/bone fracture.
 - Uncompensated/symptomatic hypothyroidism.
 - Moderate to severe hepatic impairment (Child-Pugh B or C).

5.3.13 Other severe acute or chronic medical conditions including immune colitis, inflammatory bowel disease, immune pneumonitis, pulmonary fibrosis or psychiatric conditions including recent (within the past year) or active suicidal ideation or behavior; or laboratory abnormalities that may increase the risk associated with study participation or study treatment administration or may interfere with the interpretation of study results and, in the judgment of the investigator, would make the patient inappropriate for entry into this study.

5.3.14 Major surgery (e.g., GI surgery, removal or biopsy of brain metastasis) within 8 weeks before first dose of study treatment. Complete wound healing from major surgery must have occurred 1 month before first dose and from minor surgery (e.g., simple excision, tooth extraction) at least 10 days before first dose. Subjects with clinically relevant ongoing complications per investigator clinical judgement from prior surgery are not eligible.

5.3.15 Corrected QT interval calculated by the Fridericia formula (QTcF) > 500 ms per electrocardiogram (ECG) within 28 days before first dose of study treatment.

Note: If a single ECG shows a QTcF with an absolute value > 500 ms, two additional ECGs at intervals of approximately 3 minutes must be performed after the initial ECG, and the average of these three consecutive results for QTcF will be used to determine eligibility.

5.3.16 Diagnosis of another malignancy within 2 years before first dose of study treatment, with the exception of those determined by the treating investigator to have a negligible risk of metastasis or death (such as adequately treated carcinoma in situ of the cervix, basal or squamous cell skin cancer, ductal carcinoma in situ treated surgically with curative intent, localized prostate cancer treated with curative intent and/or no intent for further treatment, or incidental prostate cancer).

5.3.17 Current use of immunosuppressive medication, EXCEPT for the following: a. intranasal, inhaled, topical steroids, or local steroid injection (e.g., intra-articular injection); b. Systemic corticosteroids at physiologic doses \leq 10 mg/day of prednisone or equivalent; c. Steroids as premedication for hypersensitivity reactions (e.g., CT scan premedication).

5.3.18 Has active autoimmune disease currently requiring systemic treatment with high dose corticosteroids (dose more than physiologic replacement doses equivalent to prednisone 10 mg daily) or disease modifying immunosuppressive agents). Replacement therapy (e.g., thyroxine, insulin, or physiologic corticosteroid replacement therapy for adrenal or pituitary insufficiency, intranasal, inhaled, topical steroids, or local steroid injection) is not considered an exclusion.

5.3.19 Active autoimmune disease that might deteriorate significantly when receiving an immuno-stimulatory agent per treating physician's clinical judgment. Subjects with diabetes type I, vitiligo, psoriasis, or hypo- or hyperthyroid diseases not requiring immunosuppressive treatment are eligible.

5.3.20 Prior organ transplantation including allogenic stem-cell transplantation.

5.3.21 Has known history of (non-infectious) pneumonitis that required steroids or has current pneumonitis.

5.3.22 Has an active infection currently requiring systemic (intravenous) antibiotic therapy.

5.3.23 Has a known history of active TB (Bacillus Tuberculosis).

5.3.24 Has known active Hepatitis B (e.g., HBsAg reactive) or Hepatitis C (e.g., HCV RNA [qualitative] is detected).

5.3.25 Has a known history of Human Immunodeficiency Virus (HIV) (HIV 1/2 antibodies).

5.3.26 Active and inactive vaccinations within 4 weeks of the first dose of pembrolizumab is prohibited.

5.3.27 Known prior severe hypersensitivity to investigational products or any component in its formulations, including known severe hypersensitivity reactions to monoclonal antibodies (NCI CTCAE v.5.0 Grade \geq 3).

5.3.28 _____ Is pregnant or breastfeeding, or expecting to conceive or father children within the projected duration of the trial, starting with the pre-screening or screening visit through 120 days after the last dose of trial treatment.

5.3.29 _____ Subjects taking prohibited medications as described in Section 6.8. A washout period of prohibited medications for a period of at least two weeks or as clinically indicated should occur prior to the start of treatment.

5.3.30 _____ Inability to swallow tablets or evidence of impaired intestinal absorption

I certify that this patient meets all inclusion and exclusion criteria for enrollment onto this study.

Investigator Signature

Date

Time

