I will provide copies of the protocol and all pertinent information to all individuals responsible to me who assist in the conduct of this study. I will discuss this material with them to ensure that they are fully informed regarding the study treatment, the conduct of the study, and the obligations of confidentiality.

This document is signed electronically through submission and approval by the Principal Investigator at Huntsman Cancer Institute in the University of Utah IRB Electronic Research Integrity and Compliance Administration (ERICA) system. For this reason, the Principal Investigator at Huntsman Cancer Institute will not have a hand-written signature on this signature page.

Instructions to multi-site Principal Investigators at locations other than Huntsman Cancer Institute: SIGN and DATE this signature page and PRINT your name. Return the original, completed and signed, to the HCI Research Compliance Office. Retain a copy in the regulatory binder.

Signature of Principal Investigator

Date

Principal Investigator Name (Print)

Name of Institution

STUDY SUMMARY

Title	Cabozantinib plus pembrolizumab as first-line therapy for cisplatin-ineligible advanced urothelial carcinoma
Short Title	CaboPembro UC
Protocol Number	IRB#104688
IND	IND#139643
Phase	Phase II
Design	Single-arm, nonrandomized phase II study to test efficacy of combination pembrolizumab and cabozantinib.
Study Duration	Accrual will take approximately 1-2 years with 1 year of treatment and 6 months follow up. Total study duration 3-4 years.
Study Centers	This study will be conducted at the Huntsman Cancer Institute and up to two additional cancer centers.
Objectives	Primary Objective: Evaluate measurable disease overall response rate (ORR). Secondary Objectives: Evaluation of progression-free survival (PFS) at 6 months (PFS6), overall survival (OS), and evaluation of toxicities of the combination.
Number of Subjects	39 subjects will be enrolled to ensure 35 evaluable patients

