Diagnosis and Main Eligibility Criteria	
Cisplatin-ineligible urothelial carcinoma
 
Key Inclusion Criteria:
 
• Histologically proven transitional cell or urothelial carcinoma (UC).• Metastatic (any N+ or M1) or locally advanced, unresectable (T4bN0) disease.• Measurable disease is required as determined by RECIST v1.1.• Cisplatin-ineligibility based on ≥ 1 of the following:
○ Estimated CrCl of between ≥ 40 and < 60 ml/min (CG formula)○ ECOG PS ≥ 2○ Hearing loss○ Baseline neuropathy○ Patient refusal 
Key Exclusion Criteria:
 
• Prior chemotherapy for metastatic/ advanced urothelial carcinoma.• Prior chemotherapy treatment for localized urothelial carcinoma that has been completed less than 6 months before registration.

	
• Small-cell or sarcomatoid component in histology.
Study Product, Dose, Route, Regimen	Pembrolizumab 200mg IV q 3 weeks with cabozantinib administered 40mg orally, with dose reductions to 20 mg daily. Subsequent dose reduction to 20 mg every other day to improve tolerability is allowed.
Duration of administration	Patients will receive therapy until treatment discontinuation criteria is met or until 12 months from start of therapy
Reference therapy	Study treatment will be compared to pembrolizumab as single agent.
Statistical Methodology	A 95% one-sided exact binomial confidence interval (Clopper-Pearson) will be calculated for ORR. With 35 evaluable subjects the lower bound of the 95% confidence interval will extend no more than 26% from the observed proportion. If there are 17 or more objective responses in 35 patients the confidence interval will exclude 32%. Secondary analyses will include an association of risk group (based on performance status and visceral metastasis) with PFS. Stratified Kaplan-Meier methodology will be used to associate risk group (based on performance status and visceral metastasis) with PFS.

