We hypothesize that the combination of cabozantinib plus pembrolizumab will be safe in cisplatin-ineligible patients as a first-line treatment. Also we hypothesize that this combination will demonstrate significant additive or synergistic activity resulting in a 20% increase in response in this disease compared to historic benchmarks for progression-free survival.

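### The trial is described as first-line, but Section 5 bars outright only prior chemotherapy for metastatic disease, cabozantinib and checkpoint inhibitors; other systemic agents need only a 2- or 4-week washout

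*Combined protocol and SAP*

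**What the plan says.** The Study Summary gives the title as "Cabozantinib plus pembrolizumab as first-line therapy for cisplatin-ineligible advanced urothelial carcinoma". The hypothesis at the end of Section 2 says that the combination "will be safe in cisplatin-ineligible patients as a first-line treatment".

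Section 5.3 deals with earlier treatment in two ways.

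- **Barred without time limit:** "Prior chemotherapy for metastatic urothelial carcinoma" (5.3.1); "Has received prior treatment with cabozantinib" (5.3.4); and any earlier checkpoint inhibitor (5.3.7).
- **Barred only within a window:** "Prior chemotherapy for localized urothelial carcinoma that has been completed less than 6 months before registration" (5.3.2); "Receipt of any type of small molecule kinase inhibitor (including investigational kinase inhibitor) within 2 weeks before first dose of study treatment" (5.3.5); and "Receipt of any type of cytotoxic, biologic, or other systemic anticancer therapy (including investigational) within 4 weeks before first dose of study treatment" (5.3.6).

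The synopsis version of 5.3.1 reads "Prior chemotherapy for metastatic/ advanced urothelial carcinoma". It adds advanced disease but still names only chemotherapy.

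Section 12 makes registration depend on meeting the requirements in Section 5. Section 11.1 plans a descriptive analysis of the objective response rate (ORR) in 35 evaluable patients, with a one-sided 95% Clopper-Pearson interval, and cites first-line gemcitabine-carboplatin results of 36% and 38.4% as background.

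**The concern.** Being first-line depends on all earlier systemic treatment for the advanced disease, not on chemotherapy alone. The protocol turns the label into criteria for chemotherapy, for one of the study drugs and for the class of the other. It leaves open every other kinase inhibitor, every biologic that is not a checkpoint inhibitor, and investigational agents.

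A patient whose metastatic disease had progressed on one of these could be certified eligible against the Section 5 checklist and counted in an ORR reported as first-line. Section 3.1.2 lists MET, VEGFR-1 to -3 and AXL among cabozantinib's targets, so an earlier inhibitor with overlapping targets could plausibly lower the chance of response. In a single-arm study the population is defined by the eligibility criteria, and the reading of the ORR rests on that definition.

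**Working it through.** **Step 1. Does any other clause close the gap?** Reading the remaining places where earlier therapy could be restricted:

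- 5.2.12 and 5.2.13 require recovery from the effects of earlier treatment. They foresee earlier therapy and do not forbid it.
- 5.3.13 is a judgement clause about medical or psychiatric conditions and laboratory abnormalities, not about line of therapy.
- 6.8.3 restricts other anticancer treatment until study treatment has been permanently stopped. It does not look back before the first dose.
- The synopsis exclusion names chemotherapy only.
- The title is not one of the Section 5 requirements that Section 12 tests.

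None closes it. Sections 5.3.1 and 5.3.2 separate metastatic from localized disease for chemotherapy; 5.3.5 and 5.3.6 make no such distinction.

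Two side observations. A kinase inhibitor is also a systemic anticancer therapy, so it falls under both 5.3.5 and 5.3.6, and the text does not say which window governs; on either reading the patient becomes eligible after washout. And 5.3.1 says metastatic where the synopsis says metastatic or advanced, although T4bN0 disease is eligible under 5.2.3.

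**Step 2. Reproduce the plan's own figure.** The lower one-sided 95% Clopper-Pearson limit for r responses in n patients is the 0.05 quantile of Beta(r, n − r + 1).

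- r = 17, n = 35: observed 17/35 = 48.6%, lower limit 33.8%, which excludes 32% as Section 11.1 states.
- r = 16, n = 35: observed 16/35 = 45.7%, lower limit 31.2%, which does not.

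**Step 3. How large could the effect be?** The documents give neither the number of pretreated patients, k, nor the deficit in their response probability, d. Both are assumed here. Expected responses lost = k × d; fall in pooled ORR = k × d / 35.

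| k of 35 | d = 5 points | d = 10 points | d = 20 points |
|---|---|---|---|
| 0 | 0 | 0 | 0 |
| 2 | 0.1 responses, 0.29 points | 0.2, 0.57 | 0.4, 1.14 |
| 4 | 0.2, 0.57 | 0.4, 1.14 | 0.8, 2.29 |
| 6 | 0.3, 0.86 | 0.6, 1.71 | 1.2, 3.43 |

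One response is 1/35 = 2.86 points. Only the corner with 6 patients and a 20-point deficit costs more than one expected response. For scale, at 17/35 the distance from the estimate to its lower limit is 48.6 − 33.8 = 14.8 points.

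**The case against.** The strongest reply is that the affected patients may not exist. The treatments that Section 2 describes in use for this disease are platinum-based and other chemotherapy and PD-1/PD-L1 agents; for metastatic disease 5.3.1 and 5.3.7 bar all of them. Kinase inhibitors in urothelial carcinoma appear only as cabozantinib, which 5.3.4 bars, and as a preclinical crizotinib model. The washouts also have proper uses: drugs given for localized disease, or for an earlier malignancy of the kind that 5.3.16 permits. All of this stands. It limits the size of the problem, but the criteria still do not say what the title says.

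Three stronger readings are tempting, and the documents do not support them.

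- **That the protocol itself documents a line-of-therapy gap in response to pembrolizumab.** A reader might set the 26% in Section 11.1 against the second-line 21.1% in Section 2. The 26% carries no line of therapy, so the difference cannot be used as a measured effect of pretreatment. For the same reason the ORR is not read purely against first-line history: the synopsis names single-agent pembrolizumab as the reference.
- **That losing one response could reverse the trial's decision at 17/35.** Section 11.1 calls the ORR analysis descriptive and gives 17/35 as a property of the interval. It attaches no action to it.
- **That the effect could never be separated out in a single-arm trial.** Medical history is collected at screening (Sections 8 and 9.2), so pretreated patients can be identified and the ORR given without them.

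**Conclusion.** The point holds as an inconsistency between the stated population and the criteria that define it. Followed exactly, Section 5 admits patients who are not first-line for metastatic or advanced disease, and no other clause prevents this. That conclusion depends on no calculation.

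The practical effect is probably small and may be nil. Under the assumed ranges it is a fall of 0.29 to 3.43 points in ORR, or 0.1 to 1.2 expected responses, with zero also compatible with the documents. The direction rests on the assumption that pretreated patients respond less often. If so, the result would understate first-line activity and would not create a false appearance of it. The change is worth making because it is specific and cheap, not because the ORR is at serious risk.

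**What to change.** 1. Reword 5.3.1 and the matching synopsis line so that both exclude any prior systemic anticancer therapy for metastatic or locally advanced unresectable urothelial carcinoma. This also removes the difference between the two texts.
2. State that the 5.3.5 and 5.3.6 washouts apply to therapy given for localized disease or another malignancy, and reconcile their overlap for kinase inhibitors.
3. For patients already enrolled, identify any such earlier therapy from the screening medical history and report ORR with and without them. If there are none, say so; that settles the matter for the reported result.

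Cost: a few otherwise eligible patients may be lost. Section 6.9 shows that the protocol has reached at least Amendment 7. Under Section 15.8 a further amendment needs approval from the cabozantinib supplier and the IRB, with FDA review if it significantly affects the study's scope or scientific quality. A change in eligibility cannot alter who has already entered, so item 3 is the part that protects the analysis if accrual is well advanced or complete.

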6 TREATMENT PLAN

Treatment should be administered on Day 1 of each cycle after all procedures and assessments have been completed as detailed on the Study Calendar (Section 8). Trial treatment may be administered up to 3 days before or after the scheduled Day 1 of each cycle.

All trial treatments will be administered on an outpatient basis.

6.1 Administration Schedule

Pembrolizumab 200 mg will be administered as a 30 minute IV infusion every 3 weeks. Sites should make every effort to target infusion timing to be as close to 30 minutes as possible. However, given the variability of infusion pumps from site to site, a window of -5 minutes and +10 minutes is permitted (i.e., infusion time is 30 minutes: -5 min/+10 min).

Cabozantinib is administered at 40 mg oral daily (with dose reductions to 20 mg daily; a subsequent dose reduction to 20 mg every other day to improve tolerability is allowed).

Therapy continues until progression or intolerable toxicities. Study treatment may continue beyond initial radiographic or clinical disease progression as long as the patient is deriving clinical benefit from the treatment, as assessed by the investigator. A safety analysis will be performed after the first 6 patients enroll and receive treatment. During this stage, the decision to continue enrollment will be made by the Data Safety and monitoring committee (DSMC), when all 6 subjects have been followed for at least 21 days following first dose of pembrolizumab and cabozantinib. All available safety data will be considered in a decision to continue enrollment. Patients removed from therapy without evidence of progression will undergo radiological examination every 12 weeks or earlier if clinically warranted.).

